YNHH Human Subjects Protection Administrator Assurance Statement

Required when the study is conducted solely at YNHH by YNHH health care providers.

As Human Subject Protection Administrator (HSPA) for YNHH, I certify that:

- I have read a copy of the protocol and approve it being conducted at YNHH.
- I agree to notify the IRB if I am aware of any real or apparent institutional conflict of interest.
- The principal investigator of this study is qualified to serve as P.I. and has the support of the hospital for this research project.

 YNHH HSPA Name (PRINT) and Signature

 Date

SECTION V: RESEARCH PLAN

1. **Statement of Purpose:** State the scientific aim(s) of the study, or the hypotheses to be tested. To test the preliminary efficacy of 16.0 mg of Prazosin daily versus placebo in treatment seeking alcohol dependent individuals. This proposal is a laboratory and treatment outcome study to examine the effects of Prazosin on brief exposure to stress, alcohol cues and neutral situations on alcohol craving, mood and neurobiological reactivity in a sample of alcohol dependent individuals. Prazosin will be beneficial for reduction in stress and alcohol cue induced craving

and related neuroadaptations. In a sample of 150 alcohol dependent men and women, we propose to examine (a) differences in measures of alcohol craving, emotion state, hypothalamic-pituitary-adrenal (HPA) activation, physiological changes and plasma catecholamine response to stress imagery and to drug cue imagery as compared to neutral imagery; (b) reduction in alcohol abstinence symptoms; and (c) improvement in alcohol treatment outcomes as measured by increasing abstinence, reduction in alcohol use and increased treatment attendance.

2. Background: Describe the background information that led to the plan for this project. Provide references to support the expectation of obtaining useful scientific data.

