with medication and alcohol withdrawal/anxiety, we used a conservative effect size of $d = .60$ for detection of significant main effects and possible interactions in the clinical trial. At this effect size and power = .80, with $p < .05$, sample size estimates from Cohen (1988, p.258) indicated that we would require 25 subjects per cell to adequately assess the proposed hypotheses for the clinical trial (total $N = 100$). Including a 15-20% drop-out after enrollment, we estimated recruitment of 120 AD patients into the trial to ensure adequate power for the trial.

Data Analysis for Laboratory Study: Repeated measures ANOVA and mixed model procedures to assess treatment group differences in alcohol craving and stress related changes (heart rate, blood pressure, HPA and catecholamine responses) during laboratory exposure to stress and drug cues as compared to neutral imagery conditions. Non-parametric tests will be used to assess occurrence of side effects, treatment retention rates, alcohol use measures, CIWA scores and perceived stress scores during the outpatient treatment phase. The number and type of AE's for the two treatment groups will be conducted using t-tests, chi-square tests and ANOVAs as appropriate. Findings will be used to estimate effect sizes for the medication and guide the larger randomized clinical trial.

Data Analysis for the 12-week clinical trial Study: For this phase, the following moderator and primary and secondary outcomes are specified:

Primary Moderator Measure: Alcohol withdrawal symptoms, as measured by the CIWA alcohol withdrawal scale,

Primary Outcome Measures in the outpatient treatment phase: These are: (1) Heavy drinking days (5 or more for men, 4 or more for women) during the 12 week period, and (2) Any drinking days. Both will be assessed daily using smartphone or interactive voice recording surveys completed by the patients and also with weekly urine drug screens/breathalyzer reports and self report of drug use on the Substance Use Calendar.

Secondary Outcome Measures in the outpatient treatment phase: Secondary outcome measures will include alcohol craving scales, anxiety (Hamilton Anxiety Scale) and depression (CES-D) and sleep quality using the Pittsburgh Sleep Quality Index – PSQI).

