Data Analytic Procedures: Since patients will be randomly assigned to the Prazosin and PLA treatment groups and Intent-to-Treat (ITT) analyses will be conducted for the clinical outcomes. We do not expect the groups to be different on demographic, prior drug use history or other predictor variables. Nevertheless, prior to undertaking the specific analysis for each aim, we will compare the treatment groups on demographic variables, substance use characteristics and previous psychiatric history/predictor variables using t-tests/chi-square analyses as appropriate. If any group differences are found, the specific variable will be entered as a covariate in all of the specific analyses. As there are no established thresholds for AW effects on drinking outcomes in outpatient treatment, baseline AW will be assessed as continuous measure in all overall analyses. Thus, intent-to-treat (ITT) analyses with baseline AW severity (mean-centered continuous CIWA-Ar scores) as a moderator of Time (Pre-Full Dose(FD): weeks 1-2; Post FD: weeks 3-12) were conducted with linear or generalized linear mixed effect (LME/GLME) piecewise growth models for continuous and binary outcomes. Due to a positive skew, number of drinks per day

(AvgD) will be log-transformed. Control variables in all analyses will be gender (0=male), inpatient (0=outpatient), and dropout (0=completer, 1=dropout/withdrawn prior to 4 weeks, 2=dropout/withdrawn after 4 weeks). For secondary outcomes linear mixed models with random intercepts will be used to assess the effect of AW, Treatment and Week (factor 1-12, or Weeks 4, 8 and 12) on the secondary outcome variables. All control variables from the main outcome analyses are included in the secondary outcome analyses. If significant interactions with AW are observed for primary or secondary outcome analyses, a median split of AW scores will be conducted to obtain Low and High AW groups and assess contrasts by treatment.

Aims and Hypotheses for Laboratory and Treatment Outcome Components: All analyses of the laboratory and the treatment components will be based on the following specific aims and hypotheses:

Specific Aim 1: To evaluate the effects of Prazosin on stress-induced alcohol craving and associated neuroadaptations in alcohol dependent individuals. Hypothesis 1: Prazosin will decrease stress-induced alcohol craving and negative emotions in the laboratory as compared to placebo.

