This aim will be tested using mixed model analysis of variance procedures for each of the following dependent measures: VAS alcohol craving scale; VAS anxiety scale; brief CCQ; DES emotions of anger, sadness and fear; heart rate, blood pressure and HPA measures of ACTH and cortisol and NE and EPI.

Specific Aim 2: To evaluate the efficacy of Prazosin versus Placebo in high alcohol withdrawal individuals on primary outcomes of: (a) heavy drinking days (HDD) over 12 week period; (b) Any drinking days (DD%).

Hypothesis 2: In high alcohol withdrawal individuals, Prazosin group will show significant reductions in HDD% and DD% during the 12 week treatment period as compared to Placebo group. No differences between medication treatment groups in the Low alcohol withdrawal individuals will be observed.

Secondary outcome measures such as alcohol craving, Anxiety, depression and sleep quality will be assessed. Findings PSS, COPE and LES scores will be examined.

SECTION VI: RESEARCH INVOLVING DRUGS, BIOLOGICS, RADIOTRACERS, PLACEBOS AND DEVICES
--

If this section (or one of its parts, A or B) is not applicable, state N/A and delete the rest of the section.

A. DRUGS, BIOLOGICS and RADIOTRACERS

1. **Identification of Drug, Biologic or Radiotracer:** What is (are) the **name(s)** of the drug(s) biologic(s) or radiotracer(s) being used? Identify whether FDA approval has been granted and for what indication(s).

Prazosin (marketed by Pfizer Inc) is an alpha-1-adrenergic agonist that is known to preferentially bind to post-synaptic alpha1-adrenergic receptors. Walker et al (2008) found that Prozaosin was effective in suppressing excessive alcohol consumption in rats, suggesting the involvement of the noradrenergic system in alcohol dependence. Simpson et al. (2007) found similar findings in a pilot trial using prozosin for treatment of alcohol dependent men and women. Prazosin therefore is an excellent candidate for treating alcohol seeking behaviors. It may also be more easily tolerated than those medications which directly modulate these transmissions.

All protocols which utilize a drug, biologic or radiotracer **not** approved by, but regulated by, the FDA, or a radiotracer regulated by the RDRC, must provide the following information:

- What is the Investigational New Drug (IND) **number** assigned by the FDA? N/A
- Who holds the IND?
- All protocols which utilize a radiotracer not approved by, but regulated by the FDA must provide the IND number: _____

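### The 80% power claim for the clinical trial does not say which contrast d = 0.60 describes; it covers Hypothesis 2 only if the drug effect in high-withdrawal patients is about twice that size

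*Combined protocol and SAP*

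**What the plan says.** Section V, item 12, Power Analysis, takes a 2x2 design (medication by alcohol withdrawal/anxiety) and a single value, d = 0.60, "for detection of significant main effects and possible interactions in the clinical trial". With power 0.80 and p < .05 it concludes that "we would require 25 subjects per cell to adequately assess the proposed hypotheses for the clinical trial", a total of 100. Allowing for 15-20% drop-out, "we estimated recruitment of 120 AD patients into the trial to ensure adequate power for the trial". The enrolment target elsewhere (Section V, items 1, 3, 5 and 7; Section VII, item 1) is 150.

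The Statement of Purpose sets an overall aim: "To test the preliminary efficacy of 16.0 mg of Prazosin daily versus placebo in treatment seeking alcohol dependent individuals". Item 12, however, introduces its aims with "All analyses of the laboratory and the treatment components will be based on the following specific aims and hypotheses", and the only clinical-trial aim listed there is Specific Aim 2: "To evaluate the efficacy of Prazosin versus Placebo in high alcohol withdrawal individuals on primary outcomes of" heavy drinking days and any drinking days. Hypothesis 2 predicts a benefit in high-withdrawal patients and adds: "No differences between medication treatment groups in the Low alcohol withdrawal individuals will be observed".

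Under Data Analytic Procedures, "baseline AW will be assessed as continuous measure in all overall analyses". The high and low groups are formed by a median split, and compared by treatment, only if an interaction with withdrawal is significant.

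**The concern.** One effect size is attached to two kinds of test and then to all the clinical hypotheses. The drug effect across all patients, the drug-by-withdrawal interaction and the drug effect within the high-withdrawal half are different contrasts with different standard errors. The same 0.60 means different things in each. The hypothesis that the aims section makes the basis of the clinical analysis is the third, reached through the second. The plan gives no assumed effect, power or detectable effect for it.

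The practical risk lies in interpretation. If Hypothesis 2 is not confirmed, a reader could take the result as coming from a test with 80% power. Whether it did depends on an assumption that the plan does not state.

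**Working it through.** **Inputs.** From the Power Analysis: d = 0.60, power 0.80, alpha 0.05, 25 per cell, four cells, N = 100. From the dosing table: equal arms. From Hypothesis 2: no effect in the low half. From the median split: equal halves. My assumptions: two-sided test, one summary outcome per patient, effects in units of the within-cell SD. Power is from the noncentral t distribution.

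**1. The plan's own figure.** Pooled comparison, n per arm, noncentrality d x sqrt(n/2):
- 50 v 50: 0.60 x sqrt(25) = 3.00, power 84.4%.
- 80% needs 45 per arm (80.4%; 44 per arm gives 79.5%), that is 90 in total, or 92 when rounded up to 23 per cell.

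So 25 per cell is slightly more than a pooled d = 0.60 requires. There is no arithmetic shortfall.

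**2. What a pooled 0.60 implies under Hypothesis 2.** With equal halves, pooled effect = (d_high + d_low)/2. Setting d_low = 0 gives d_high = 2 x 0.60 = 1.2. At N = 100:
- 2x2 interaction: the difference between the two drug effects is 1.2, its SE is sqrt(4/25) = 0.40, and 1.2/0.40 = 3.00, so power is 84.4%.
- High-half contrast, 25 v 25: 1.2 x sqrt(12.5) = 4.24, power 98.6%.

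**3. If 0.60 is the effect in the high half and 0 in the low half.** High-half noncentrality is 0.60 x sqrt(N/8). Interaction noncentrality is 0.60/sqrt(16/N).

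| N analysed | High-half contrast | 2x2 interaction | Detectable high-half d at 80% (contrast alone) |
|---|---|---|---|
| 100 | 55% | 32% | 0.81 |
| 120 | 63% | 37% | 0.74 |
| 150 | 73% | 45% | 0.66 |

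For the contrast alone, 80% power at 0.60 takes 45 per arm within the high half, or 4 x 45 = 180 analysed. With the plan's 15-20% drop-out, 120 recruited leaves 120 x 0.85 = 102 to 120 x 0.80 = 96, so the first row is the one closest to the Power Analysis.

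**4. Sensitivity of the contrast (100/120/150 analysed).** High-half d = 0.50: 41%/48%/57%. High-half d = 0.80: 79%/86%/93%. High-half d = 0.60 with an assumed 25% cut in residual variance, so 0.60/sqrt(0.75) = 0.693: 67%/75%/84%.

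**5. Interaction test first, then the contrast.** This was simulated from a simplified model: one outcome regressed on drug, a normally distributed continuous withdrawal score and their product, followed by a t test in the upper half. Probability that both steps are significant:
- High-half effect 1.2, low half 0, N = 100: about 62% if the effect jumps at the median. If it rises linearly with withdrawal, averaging 1.2 above the median and about 0 below, about 93%.
- High-half effect 0.60, low half 0, N = 100/120/150: about 18%/22%/27% (step) or 33%/41%/52% (linear).

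The joint figure depends heavily on the shape of the moderation, about which the plan says nothing.

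**6. Minor: the pilot w.** For 6/7 v 4/10 abstinent, chi-square = 17 x (6x6 - 1x4)^2/(7 x 10 x 10 x 7) = 17 x 1024/4900 = 3.55, so w = sqrt(3.55/17) = 0.46. The stated 1.23 cannot be w for a 2x2 table, where w cannot exceed 1. It does not enter the sample size.

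**The case against.** The best defence is that the plan is coherent on one reading. The Power Analysis names interactions as well as main effects, and with a null low half a pooled 0.60 is the same state of affairs as a high-half effect of 1.2. One number then serves both tests, and N = 100 is adequate for the pooled effect, the 2x2 interaction and the high-half contrast. The low figures in step 3 belong to a scenario with a pooled effect of 0.30, half of what the plan assumes. All of this stands. The difficulty is that the plan never says it means this reading, and even then the two-step sequence reaches 80% at N = 100 under one of the simulated shapes and not under the other.

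It is also fair that the planned analysis is a piecewise mixed model with daily outcomes, covariates and withdrawal as a moderator of time. The documents give no variances or correlations, so its power cannot be computed from them. The stated purpose is preliminary efficacy, which softens the consequence.

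Four stronger readings are tempting and are not supported:
- That 25 per cell is a miscalculation. For a pooled 0.60 it is more than enough.
- That the trial has only 55% power for Hypothesis 2. This assumes that 0.60 is the high-half effect, which the plan does not say.
- That 0.60 is not conservative because it implies 1.2 beside the pilot's 1.26. That sets a subgroup effect against a whole-sample one; like for like, 0.60 is about half of 1.26.
- That the 120 v 150 discrepancy weakens power. The larger target raises it; what is unclear is which number the statement covers.

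**Conclusion.** The concern holds as a gap in the power statement, not as proof that the trial is too small. The 80% claim is attached to the clinical hypotheses as a whole, but for Hypothesis 2 it is borne out only if the high-withdrawal effect is about 1.2 with a null low half, an assumption the plan leaves unstated. If the effect there is 0.60, the high-half contrast has 55% to 73% power and the 2x2 interaction 32% to 45%, across 100 to 150 analysed. Those figures rest on equal halves and arms, a two-sided 5% test and one summary outcome per patient. The joint figures rest in addition on a simplified simulation and should be taken as indicative only. That the contrast is undefined is certain; the trial's actual power for Hypothesis 2 is not known from the documents. This should be fixed.

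**What to change.** Restate the power by contrast in Section V, item 12:

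1. Say that 25 per cell gives at least 80% power for a pooled effect of d = 0.60, equivalent to d = 1.2 in the high-withdrawal half when the low half is null.
2. For the Hypothesis 2 contrast, alone and after the significant-interaction condition in Data Analytic Procedures, give the assumed effect in each half, the assumed shape of moderation, the variance assumptions, and the resulting power or detectable effect. For the contrast alone, the simple calculation gives a detectable d of about 0.81, 0.74 or 0.66 at 100, 120 or 150 analysed.
3. State whether the power statement applies to 120 or to 150 recruited, and how many are expected in the analysis.
4. Minor: check or relabel the pilot w of 1.23.

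The cost is wording and a short calculation. No extra patients and no change of design are needed. The drawback is that the stated power for Hypothesis 2 may be less favourable than the present text suggests.

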One hundred and fifty treatment seeking alcohol dependent individuals (men and women) will be recruited to participate in this medication study. Subjects may or may not participate in laboratory sessions. Subjects will be recruited through flyers and advertisements in local newspapers and from community substance abuse treatment facilities. Subjects will participate in an initial screening and intake session to obtain informed consent, followed by physical examination and blood work to determine eligibility. Subjects will be randomized to Prazosin (PRZ) or placebo (PLA) and medication will be dispensed in a three times daily dosing schedule (t.i.d. dosing) with 5 mg in the morning, 5 mg in the afternoon and 6 mg at night reached at the end of the 2-week period, and maintained at this or their highest tolerated dose until week 11, followed by a 5-day taper in week 12, as in previous research. The titration schedule was as follows: 1 mg dose at bedtime for 2 nights, followed by a 1mg dose morning and night (8 AM/8 PM) on day 3, then 2 mg dose t.i.d., on days 4-6, 3 mg dose (2 pills each) morning and afternoon, and 4 mg dose (2 pills) at night for days 7-9, increased to 4 mg dosing t.i.d. on days 10-13, and from day 14 through week 11, 5 mg (1 pill) each in the morning and afternoon, and 6 mg for the night (2 pills) dose. Subjects will be maintained on this dose during the laboratory sessions (if completing the laboratory sessions) and until week 12 of the study at which point they will be tapered off the study medication over the course of five days. Some subjects may be tapered prior to completion of the 12 weeks. This taper is similar to what has been used with lofexidine in opiate withdrawal protocols (Bearn et al., 1996; Strang et al., 1997) and in our outpatient relapse prevention study of lofexidine with opiate dependent patients. We expect most subjects will tolerate a daily dose of 16.0mg. However, subjects who cannot tolerate a dosing schedule of 16.0 mg will meet with the study psychiatrist to discuss a reduction in dose down to 10mg/day. Based on the Physician Desk Reference (2007), which reports that dosage may be as high as 40mg daily, we anticipate that 16.0mg per day will be well tolerated by subjects. Subjects who cannot tolerate a minimum dose of 6mg/day will be removed from the study protocol.

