Subjects will complete a variety of diagnostic, cognitive and psychological assessments, a comprehensive physical examination and blood work. If completing the laboratory component as inpatients, subjects will also be involved in development of imagery scripts from personal stress, drug-related cue and neutral situations during the first 3 weeks of their stay. After subjects have been substance- free for 21+ days, they will participate in an imagery/relaxation training and

habituation session. Between weeks 3 – 4, subjects will participate in a 3-day experiment in which during a 2-hour laboratory session on three consecutive days, subjects will be exposed by guided imagery to a personal stressful situation, a drug cue related situation and a neutral relaxing situation, one exposure per day. Order of imagery type will be randomly assigned across subjects.

Research Plan:

Subjects will have the option of participating in either the inpatient–outpatient plan, or the outpatient plan. The inpatient–outpatient plan involves 3 - 4 weeks of inpatient treatment followed by 8 - 9 weeks of outpatient treatment. Subjects completing the inpatient-outpatient plan may or may not complete the laboratory sessions. The outpatient plan involves outpatient treatment with 12-Step Counseling for 12 weeks. Subjects enrolled in the outpatient plan also have the option to complete 4 days of inpatient laboratory sessions. The provision of an outpatient alternative is added to provide an opportunity for participation to those subjects who are not able to participate in longer inpatient treatment due to childcare, employment, or other related obligations. The three alternatives are described below:

Inpatient-Outpatient Plan with laboratory sessions:

Once a subject is deemed eligible, those who are interested in the inpatient option will be admitted to the Clinical Neuroscience Research Unit (CNRU) of the Connecticut Mental Health Center (CMHC) for the 3 - 4 week stay that will involve medication initiation and laboratory sessions where subjects will be exposed to stress, drug cues and neutral-relaxing cues on three separate consecutive days. Lab sessions will take place either on the Clinical Neuroscience Research Unit (CNRU) or at the Yale Stress Center.

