After completing the inpatient phase of the study, subjects will either taper off the study medication or participate in a 9-week outpatient medication trial. Those choosing to continue treatment will be seen 2 times per week in outpatient treatment at the Substance Abuse Center at CMHC, or at the Yale Stress Center at [name]. Subjects will be maintained on 16.0mg dose of PRZ/PLA until week 12. In week 12, subjects will undergo a 5-day taper similar to what has been used with Lofexidine in opiate withdrawal protocols (Bearn et al., 1996; Strange et al., 1997) and in our outpatient relapse prevention study of Lofexidine and Guanfacine with opiate and cocaine dependent patients respectively. Urine monitoring, assessment of craving, alcohol abstinence symptoms, self report of drug use and stress and craving scales, heart rate and blood pressure will be assessed weekly in the trial.

Inpatient-Outpatient Plan without laboratory sessions:

The plan for subjects completing the Inpatient-Outpatient Plan without laboratory sessions, will be identical to the plan for the Inpatient-Outpatient Plan with laboratory sessions, minus the laboratory sessions, and all procedures related to the laboratory sessions, such as participating in imagery script development sessions. Once a subject is deemed eligible, those who are interested in the inpatient option will be admitted to the Clinical Neuroscience Research Unit (CNRU) of

the Connecticut Mental Health Center (CMHC) for the 3 - 4 week stay that will involve medication initiation.

After completing the inpatient phase of the study, subjects will either taper off the study medication or participate in a 9-week outpatient medication trial. Those choosing to continue treatment will be seen 2 times per week in outpatient treatment at the Substance Abuse Center at CMHC, or at the Yale Stress Center at [name]. Subjects will be maintained on 16.0mg dose of PRZ/PLA until week 12.

Outpatient Plan:

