Simpson et al (2007) report that when administering 16mg per day of the drug, blood pressure changes were more evident in the prazosin group; however, the drop was still within the normal range. Raskind et al. 2002, prescribed up to 20mg a day of the study medication. Three of the 36 subjects reported orthostatic dizziness, headache, and lethargy, however no subject experienced syncope or a fall. The researchers report that previous administration of Prazosin for hypertension and benign prostate hypertrophy has shown that adverse effects tend to occur at initial lower doses rather than at higher doses. Raskind et al, 2007 used a maximum dosage of 15mg which was maintained for 8 weeks. No significant differences in supine or standing blood pressure were found between the placebo and Prazosin groups. Transient dizziness was reported by some subjects, however, most of these subjects were also receiving concurrent antihypertensive or psychotropic medication, and was also reported by subjects in the placebo group. Therefore, it appears that a maximum maintenance dosage of 16mg of prazosin will be generally tolerable and safe for use in the proposed adult sample of subjects.

3. **Source:** a) Identify the source of the drug or biologic to be used.

Commercially available Prazosin capsules will be used. Prazosin HCl (generic) is marketed by Mylan Pharmaceuticals Inc in capsules containing 1mg, 2mg, or 5mg of prazosin as the hydrochloride. The placebo medication will be prepared by the CMHC pharmacist. Both the Prazosin and the placebo will be dispensed by the CMHC pharmacist / YNHH IDS.

Prazosin pills will be purchased through the CMHC pharmacy / YNHH IDS, and the research pharmacist will make up identical active and placebo capsules for medication administration. Subjects will be randomly assigned to three times daily dosing of Prazosin/placebo (with the exception of day 1 which is once daily, and days 2-3 twice daily).

During weeks 1-4, inpatient subjects will self-administer study medication three times daily under supervision by nursing staff on the CNRU who will also monitor vital signs three times daily and side effects. Urines, alcohol craving, abstinence symptoms, mood and perceived stress scale and side effects will be assessed three times weekly.

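### As written, side effects and retention are tested only in the outpatient treatment phase, so the window differs by treatment plan and leaves out ward titration and ward exits

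*Combined protocol and SAP*

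**What the plan says.** The analysis text has two consecutive safety sentences in Section V, item 12, under Data Analysis for Laboratory Study.

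- The first applies non-parametric tests to "assess occurrence of side effects, treatment retention rates, alcohol use measures, CIWA scores and perceived stress scores during the outpatient treatment phase".
- The second reads: "The number and type of AE's for the two treatment groups will be conducted using t-tests, chi-square tests and ANOVAs as appropriate". It names no phase.

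The schedule comes from Section V, item 3 (Research Plan). "The inpatient–outpatient plan involves 3 - 4 weeks of inpatient treatment followed by 8 - 9 weeks of outpatient treatment". The ward period is described as a "3 - 4 week stay that will involve medication initiation and laboratory sessions", so inpatient-plan subjects take their first dose on the ward. Full dose applies "from day 14 through week 11, 5 mg (1 pill) each in the morning and afternoon, and 6 mg for the night (2 pills) dose". After the ward, "subjects will either taper off the study medication or participate in a 9-week outpatient medication trial". Outpatient-plan subjects follow the same titration during their 12 weeks of outpatient treatment.

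On the timing of side effects, Section VI, A.2 reports from earlier use in hypertension and prostate disease that "adverse effects tend to occur at initial lower doses rather than at higher doses". On data collection, Section VI, A.3 states: "During weeks 1-4, inpatient subjects will self-administer study medication three times daily under supervision by nursing staff". That section has the ward nurses monitor side effects and provides for side-effect assessment three times weekly. The Safety and Side Effects Measures part of Section V, item 3 treats adverse events and side effects as one item, recorded throughout the study.

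**The concern.** The phase limit takes in different parts of treatment depending on which plan a subject chose. An outpatient-plan subject is observed from the first dose. An inpatient-plan subject is observed only from week 4 or 5 onward, after the dose increases are over. The protocol itself reports that adverse effects tend to come during those early doses.

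Retention raises a separate problem. A subject removed on the ward, or who tapers at the end of the stay, has no outpatient time. A retention rate confined to the outpatient phase cannot count that subject as a failure and may leave the subject out of the denominator. The arms compared are then subsets defined by something that happens after randomisation, and tolerability could affect who is in them.

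Increased treatment attendance is among the stated purposes of the study (Section V, item 1), and item 12 says the findings will guide a larger trial. A distorted tolerability or retention figure could therefore be carried forward.

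**Working it through.** The plan gives no figure for this point, so the check is a day count followed by a comparison of passages.

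**1. Does any inpatient titration fall in a literal outpatient phase?**

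- Inputs: full dose on dosing day 14 (Research Plan and its dosing table); ward stay 3-4 weeks, or 21-28 days (Research Plan); trial length 12 weeks, or 84 days; detoxification before dosing typically 1-4 days, rarely up to a week (Section V, item 11).
- Stay day on which full dose is reached = 14 + detoxification delay. Delays of 0, 1, 4 and 7 days give stay days 14, 15, 18 and 21. All are within 21, so no titration day falls after discharge.
- Ward time left out: 21/84 = 25% to 28/84 = 33% of the 12 weeks. The outpatient part is 63 to 56 days.
- Full-dose time also left out: with no delay, 21 - 14 = 7 to 28 - 14 = 14 days. With a 7-day delay and a 21-day stay it is about 0. The range is therefore about 0-2 weeks.
- An outpatient-plan subject loses no days.

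**2. Who is left out altogether?** Two groups of inpatient-plan subjects have no outpatient time: those who taper after the stay, and those removed on the ward. Neither number is given.

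**3. Does another analysis recover them?**

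| Item | Other provision in the plan | Recovered? |
|---|---|---|
| Events on the ward | Adverse-event comparison by arm, no phase limit | Probably, but period not stated and side effects not distinguished from adverse events |
| Retention on the ward | Dropout before 4 weeks, coded under Data Analytic Procedures | No: a control variable, not an outcome compared by arm |
| Drop-out definition | Four consecutive missed research appointments (Research Plan) | No: does not describe removal on the ward |
| Intention-to-treat statement | Covers clinical outcomes | Unclear: does not say whether it overrides the phase limit |

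**4. Illustrative worst case for the phase-restricted test alone.** The inputs are assumptions except the 75 per arm in the dosing table. Assume side-effect rates in titration of 20% v 5%, no events later, an uncorrected chi-square test at two-sided 0.05, and exact binomial power. Observable rate = (1 - inpatient share) x rate.

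| Inpatient share | Observable rates | Power | Power if a further 10% v 2.5% have later events |
|---|---|---|---|
| 0% | 20% v 5% | 83% | 93% |
| 25% | 15% v 3.8% | 70% | 88% |
| 50% | 10% v 2.5% | 50% | 79% |
| 75% | 5% v 1.3% | 24% | 67% |

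The last column assumes that later events are independent of titration events and that everyone reaches the later period. For example, at a 50% share the rates become 1 - 0.90 x 0.90 = 19% v 1 - 0.975 x 0.975 = 4.9%. None of these figures applies to the unrestricted adverse-event comparison.

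**The case against.** The strongest reply is that the phrase may not mean what it says. Item 12 introduces the primary outcomes as belonging to the outpatient treatment phase and then defines heavy drinking days over the 12-week period. Data Analytic Procedures models weeks 1-2 as the period before full dose and adjusts for inpatient status, so ward weeks appear to be in the outcome analysis. In a paragraph about laboratory sessions, the phrase could simply mean the treatment trial as opposed to the imagery sessions. It also ends a list of five measures, so its attachment to side effects can be questioned.

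This shows that the window is unclear, but it does not settle the matter. Elsewhere the protocol keeps the phases apart: the Research Plan places a 9-week outpatient trial after the inpatient phase, Minimizing Risks sets different vital-sign schedules for each, and the payment section covers subjects who complete only the inpatient phase. The literal reading is available, and an analyst could follow it.

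A reader might infer that adverse events in titration are never tested. The documents do not support that, because the second safety sentence has no phase limit and the data are collected throughout. A reader might also infer that the comparison keeps those who tolerated titration and drops those who did not, so that prazosin is bound to look better tolerated. That goes too far as well. The protocol provides for subjects who cannot tolerate full dose to continue on a lower one, removal applies only below a stated minimum (Research Plan), and the taper after the ward is set against choosing to continue rather than described as an exit for intolerance.

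Finally, the statement about early adverse effects is a second-hand report from other indications, not a prediction for this sample.

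**Conclusion.** The point holds in a limited form. Followed as written, the first safety sentence uses a window that differs by plan. It omits all titration and 25-33% of the 12 weeks for inpatient-plan subjects, and it omits entirely those with no outpatient time. Two overlapping safety analyses could then cover different periods and disagree.

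The retention part is the firmer one. The adverse-event sentence does not cover retention, and early dropout enters the plan only as a covariate.

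The day count rests on the stated stay and titration schedule and holds for detoxification delays up to 7 days. The effect on the results cannot be sized from the documents. Prazosin could look better tolerated or better retained than it was; nothing shows that it would. The power figures are a worst case under assumed rates and inpatient shares, and they soften considerably once some later events are allowed.

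This should be corrected, but it is not a failure of safety testing as a whole.

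**What to change.** For side effects and retention, replace the outpatient-phase limit with one window for every plan: from first dose, on the ward or in the clinic, to the last visit after the taper. Analyse all randomised and dosed subjects by assigned arm. State the same window for the adverse-event comparison, and say whether side effects and adverse events are one measure or two.

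Summarise weeks 1-2 separately from weeks 3-12, the split already used in Data Analytic Procedures. Count removal or withdrawal on the ward as non-retention in the analysis, and state in advance how subjects who taper by choice after the stay are counted.

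The cost is a small edit to the analysis text and a little more analysis work on side-effect data already collected. The tolerability or retention figure may come out slightly less favourable. No dosing, removal or other clinical rule changes.
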